1. SYNOPSIS

Primary Study Objective	To compare gene expression stimulated by a semi-permanent filler and a biostimulator via punch biopsy
Secondary Study Objective	To assess and compare volume change in the nasolabial fold via clinical photography
Methodology	Randomized, single-center, comparative study
Number of Subjects	20 subjects to complete (10 subjects per treatment product group)
Study duration	13 weeks total
Study treatment products	Sculptra® - poly L-lactic acid (PLLA) biostimulator Radiesse® (+) – calcium hydroxylapatite (CaHA) semi-permanent filler
Conditions of use	Per on-label instruction
Study visits	Visit 1 (Day 0/baseline), visit 2 (day 5), visit 3 (day 28/week 4), visit 4 (day 84/week 12), and visit 5 (day 89).
Specific Inclusion Criteria:	
 ○ Demographics and study skin conditions 
 - Any race and ethnicity (to be recorded) - Fitzpatrick skin type (to be recorded) - Women or men - Age: 22-50 years old - Subject with a minimum of shallow nasolabial fold (NLF) contour deficiencies as assessed via the wrinkle assessment scale (WAS) - Subject with identical WAS scores on both NLFs - Subject who in the opinion of the treating Investigator would only need 2 treatments for optimal clinical outcomes - Subject with healthy immune systems ○ Administrative 
 - Ability of giving consent for participation in the study - Agreement to have skin biopsies on NLFs

	
 - Agreement to adhere to the procedures and requirements of the study and to report to the institute on the day(s) and at the time(s) scheduled for the assessments

Specific Exclusion Criteria:
	
 ○ Skin conditions - Significant NLF asymmetry, or different WAS score on each NLF - Pregnant, planning pregnancy during the course of the study or breastfeeding - History of allergy or hypersensitivity to any ingredient of the treatment products - History of allergy or hypersensitivity to anesthetics or lidocaine - Have been diagnosed with a bleeding disorder - Have experienced excessive bleeding after other medical procedures - Currently taking blood-thinning medications (e.g., aspirin, aspirin-containing medications, warfarin or heparin), prescription facial wrinkle therapies or topical steroid applied to the NLF, immunosuppressive medications or systemic steroids. - Currently taking supplements or homeopathic medications - History of skin infections, such as impetigo - History of keloid formation or hypertrophic scarring - Previous permanent or semi-permanent implant (including polylactic acid, polymethyl methacrylate and silicone) in proposed treatment area - Previous resorbable and permanent fillers, hyaluronic acid or botulinum toxin injections in the proposed treatment area within 12 months prior to the baseline visit - History of other facial treatment/procedure in the previous 12 months that would potentially interfere with study outcome (e.g., facial surgery, oral surgery, resurfacing, mesotherapy, lipolytic injections) - History of facial nerve palsy - Subject who is a smoker

Procedure
	
 ○ Visit 1 (D0/Baseline) - Subjects will be screened on the basis of the selection criteria for study qualification. - Subjects will be randomized to each treatment group and biopsy side.

	
 - Subjects will report to the site as D0 visit, will be given an informed consent form, HIPAA form, photography release form, and medical history form to complete. - 3D standardized photography will be performed on full global face. - A 3-mm punch biopsy will be performed on one side of enrolled subject's nasolabial fold accordingly pre-determined randomization. - Investigator will inject the assigned treatment product to both of the subject's nasolabial folds, based on the predetermined randomization and the treatment products' instruction to achieve the optimum correction. 
 ○ Visit 2 (D5) - Subjects will return to the site to remove surgical stitch at the biopsy site. 
 ○ Visit 3 (D28/W4) - All subjects to return to the site for follow-up. - Photography will be performed similarly to D0. - Subjects in PLLA group to have an additional treatment to both nasolabial folds. - Subjects in CaHA group to have an optional touch-up based on the Investigator's assessment. 
 ○ Visit 4 (D84/W12) - All subjects to return to the site for follow-up. - Photography will be performed similarly to D0. - A 3-mm punch biopsy will be performed on the opposite of the subject's nasolabial fold from D0. 
 ○ Visit 5 (D89) - All subjects will return to the site to remove surgical stitch at the biopsy site. - Investigator will assess the biopsy areas and offer an optional laser treatment (one or both sides) to minimize scar formation upon study completion.

Biopsy analysis
	
 - Gene expression assessing the following biomarkers: scar tissue formation, collagen, elastin, extracellular matrix integrity, epidermal barrier, anti-aging, antioxidant, cell renewal/regeneration, inflammation, growth factor, hydration.

Statistical analysis
	
Comparison of gene expression and imaging analysis between the treatment products.

3. LIST OF ABBREVIATIONS AND DEFINITIONS OF TERMS

AE	Adverse Event
°C	Degrees Celsius
CaHA	Calcium Hydroxylapatite
CRF	Case Report Form
etc.	et cetera
e.g.	for example (Latin; exempla gratia)
°F	Degrees Fahrenheit
GCP	Good Clinical Practice
HIPAA	Health Insurance Portability and Accountability Act of 1996
ICH	International Conference on Harmonization
ICT	Information and communication technologies
i.e.	that is (Latin; id est)
IEC	Independent Ethics Committee
IFU	Instruction for Use
IRB	Institutional Review Board
N or n	Number
NLF	Nasolabial fold
PLLA	Poly L-lactic acid
%	percent
SAE	Serious Adverse Event
SD	Standard deviation
SOP	Standard Operating Procedure
SWFI	Sterile water for injection
UPT	Urine Pregnancy Test

Protocol GLI.04.US.SL.020

CONFIDENTIAL

4. BACKGROUND AND RATIONALE

During aging, the skin undergoes significant changes that are often characterized by dermal thinning, redistribution of fat, and loss of skin elasticity and collagen.^{1, 2} Various factors can considerably accelerate this aging process, including environmental exposure, leading to rhytids, wrinkles, and skin laxity. There has been an increase in popularity of soft-tissue injectables as they are non-invasive and are effective for restoring lost volume and for correcting contour deficiencies to the aging face.³ Among them are two well-known injectable agents: Sculptra® (Galderma, New Jersey, USA) and Radiesse® (+) (Merz Pharmaceutical, Wisconsin, USA). Sculptra® is a poly-L-lactic acid (PLLA) biostimulator and Radiesse® (+) is a calcium hydroxylapatite (CaHA) filler. Both treatments are currently FDA-approved in the United States for correction of facial wrinkles and folds. Both provide a delayed but progressive volumizing effect by stimulating the regeneration of endogenous collagen overtime.^{4, 5}

As such, a similar mechanism of action of these injectables represents an interesting line of examination, particularly in the context of cellular activities occurring at the genomic level that contributes to neocollagenesis and potentially other structural integrity of the extracellular matrix. This study is conducted to examine the effect of PLLA and CaHA injectables in the treatment of nasolabial folds (NLFs).

5. STUDY OBJECTIVES AND CLINICAL HYPOTHESIS

5.1 Study Objectives

The primary objective of this study is to compare gene expression stimulated by a semi-permanent filler and a biostimulator via punch biopsy.

The secondary objective of this study is to assess and compare volume change in the NLF via clinical photography.

5.2 Clinical Hypothesis

When each treatment is injected to the skin, it triggers a series of biochemical reactions and inflammatory responses that contribute to the production of collagen and other protein structures in the extracellular matrix. The result is an aesthetic increase in skin volume at the treated facial area.

6. SELECTION AND DISPOSITION OF STUDY POPULATION

6.1 Number of Subjects

An appropriate number of subjects meeting inclusion/exclusion criteria listed below will be enrolled on the study to achieve maximum 20 subjects who complete the study as planned.

6.2 Study Population Characteristics

Males and females of any skin type with diagnosis of NLF contour deficiency.

6.3 Inclusion Criteria

1. Subjects of 22 to 50 years of age.
2. Subjects clinically diagnosed with a minimum of shallow NLF contour deficiency based on the wrinkle assessment scale (WAS, see section 10.1).

Protocol Version: 04

This document contains confidential, proprietary information.

Protocol GLI.04.US.SL.020

CONFIDENTIAL

3. Subjects with identical WAS scores on both NLFs (see section 10.1).
4. Subjects who in the opinion of the Investigator would only need 2 treatments for optimal clinical outcomes.
5. Subjects of any gender.
6. Subjects of any race and ethnicity.
7. Subjects of any Fitzpatrick skin type.
8. Subjects with healthy immune systems.
9. Subjects who are able and willing to provide written informed consent prior to any study related procedures.
10. Subjects who agree to be photographed at each visit.
11. Subjects who agree to have a 3-mm punch biopsy on each NLF.
12. Subjects apprised of the Health Insurance Portability and Accountability Act of 1996 (HIPAA) and applicable state Bill of Rights.
13. Subjects who agree to adhere to the procedures and requirements of the study, to report to the institute on the day(s) and at the time(s) scheduled for the assessments, and to complete all required visits.

6.4 Exclusion Criteria

1. Subjects with significant NLF asymmetry, or different WAS score on each NLF (see section 10.1)
2. Subjects who are current smokers or consume nicotine (e.g., cigarettes, e-cigarettes, vaping device with pre-filled pods, vapor tank or mod, chewing tobacco).
3. Subjects with any diseases, condition or presentation that, in the opinion of the Investigator, may put the subject at risk, may confound study results, or may interfere with participation in the study.
4. Subjects who are pregnant or breast-feeding, or who plan to become pregnant or breast feed during the course of the trial, confirmed by urine pregnancy test (UPT).
5. Subjects that are relatives of the Investigator or are themselves or a relative of any study staff or any Galderma employee.
6. Subjects who have participated in an investigational study within 30 days of enrollment; participated in biologic investigational studies within 90 days of enrollment, or subjects planning to participate in any other interventional clinical research study while enrolled in this trial.
7. Subjects with an active skin infection, such as impetigo.
8. Subjects with history of keloid formation or hypertrophic scarring.
9. Subjects with history of facial nerve palsy.
10. Subjects with history of epilepsy.
11. Subjects with history of migraine.
12. Subjects with history of allergy or hypersensitivity to lidocaine and/or any ingredient in the treatment products (PLLA, sodium carboxymethylcellulose, non-pyrogenic mannitol, CaHA, glycerin, and sterile water for injection (SWFI)).
13. Subjects with previous permanent or semi-permanent implant (including polylactic acid, polymethyl methacrylate and silicone) below the level of zygomatic arch.
14. Subjects resorbable and permanent fillers, hyaluronic acid or *botulinum toxin* injections below the level of zygomatic arch within 12 months prior to Visit 1.
15. Subjects with history of other facial treatment/procedure at the study area (NLF) in the previous 12 months that would potentially interfere with study injections (e.g., facial surgery, oral surgery, resurfacing, mesotherapy, lipolytic injections).
16. Subjects with diagnosis of a bleeding disorder.

Protocol Version: 04

This document contains confidential, proprietary information.

17. Subjects who take prescription facial wrinkle therapies or topical steroid applied in the NLF within 4 weeks of Visit 1.
18. Subjects who take immunosuppressive medications or systemic steroids (i.e., oral prednisone) within 6 months of Visit 1. Intranasal or inhaled steroids are acceptable.
19. Subjects who, at the discretion of the Investigator, have experienced excessive bleeding after other medical procedures.
20. Subjects who are currently taking concomitant medications that have the potential to prolong bleeding times such as anticoagulants or inhibitors of platelet aggregation (e.g., aspirin, aspirin-containing medications, warfarin, heparin, other nonsteroidal anti-inflammatory drugs, vitamin E, estrogen preparations, herbal supplements or homeopathic medications known to affect coagulation).

6.5 Concomitant Therapies

All treatments and therapies used 30 days prior to enrollment (visit 1/Day 0) or 90 days prior to enrollment for biologics and all treatments or therapies used during the course of the study must be recorded in the Case Report Form (CRF) or electronic Case Report Form (eCRF).

6.5.1. Authorized Therapies

Unless listed under the exclusion criteria (Section 6.4) or in Prohibited Therapies (Section 6.5.2), other therapies to treat ongoing conditions are authorized.

6.5.2. Prohibited Therapies

None other than as specified in the Inclusion/Exclusion criteria.

The decision to administer a prohibited medication/treatment should be made with the safety of the subject being the primary consideration. Whenever possible, Galderma Laboratories, L.P. should be notified before the prohibited medication/treatment is administered to discuss possible alternatives.

If a subject receives prohibited therapy during the study, the subject may be allowed (at the discretion of the Investigator / Galderma Laboratories, L.P.) to continue in the study for safety evaluation purposes, only.

7. STUDY TREATMENT

The term “study treatment” refers to the study products (see Section 7.1)

7.1 Study product Identification and Use

Study product: Sculptra®	
Form	Lyophilized PLLA with sodium carboxymethylcellulose, non-pyrogenic mannitol.
Mode of administration	Injection following reconstitution
How supplied	Sterile freeze-dried preparation in a clear glass vial, which is sealed by a penetrable stopper, covered by an aluminum seal with a flip-off cap.
Lot numbers	To be added upon study completion

Storage and handling	Store under controlled room temperature conditions, up to 30°C (86°F). DO NOT FREEZE. Refrigeration is not required.
----------------------	--

Study product: Radiesse® (+)	
Form	Opaque, sterile, non-pyrogenic, semi-solid, cohesive implant whose component is synthetic CaHA suspended in a gel carrier of glycerin, sodium carboxymethylcellulose, 0.3% lidocaine hydrochloride, and sterile water.
Mode of administration	Injection
How supplied	Individual treatment syringe with needle
Lot numbers	To be added upon study completion
Storage and handling	Store at controlled room temperature between 15°C and 32°C (59°F and 90°F).

7.2 Additional Products and Materials

The Sponsor will provide Sculptra® and UPTs for the study. The study overhead will cover any additional materials or supplies.

7.3 Study Product Accountability

Upon receipt of the study products, the Investigator or designee will conduct an inventory. In accordance with federal regulations, the Investigator must agree to keep all test article in a secure location with restricted access. Designated study personnel will provide the test article to the subjects in accordance with the protocol.

During the study, the Investigator must maintain records of study treatment dispensation and collection for each subject. This record must be made available to the study monitor for the purposes of verifying the accounting of clinical supplies. Any discrepancies and/or deficiencies between the observed disposition and the written account must be recorded along with an explanation. At the conclusion of the study, the Investigator will be responsible for returning all unused study product (i.e., Sculptra®) unless otherwise instructed by the Sponsor. Shipping label and cost will be provided to the Investigator by the Sponsor.

7.4 Study Product Preparation

Each PLLA vial will be reconstituted by adding 8 mL of SWFI and 1 mL of 2% lidocaine to obtain a total of 9 mL of injectable preparation. Reconstitution description can be found in the Instruction for Use (IFU).

CaHA is supplied in sterile individual treatment syringes packaged with fine gauge needles. Reconstitution is not needed.

7.5 Method of Treatment Assignment

Before the start of the study, a randomization list will be prepared by the Sponsor utilizing a computer-generated software. This will randomly assign the study product to each enrolled subject and the NLF side for punch biopsy.

7.6 Treatment Dosage and Mode of Administration

The injection technique (skin disinfection material, type of syringe, type and gauge of the intradermal needle, penetration angle, depth) will be the technique customarily used by the Investigator. The type of gauge of the injection needle will be recorded in the CRFs.

PLLA: two treatment sessions at 4-week interval with the first treatment at Visit 1 and the second treatment at Visit 3. Each treatment session will be consisted of multiple deep dermal injections, up to 9 mL/session (or up to 4.5 mL/NLF/session), into the left and right NLFs of each subject according to the IFU. The treatment amount for each PLLA subject will be determined at the Investigator discretion to achieve an optimal correction. Within each PLLA subject, the amount of each treatment needs to be equal at the left and right NLFs because of the identical WAS scores. The treatment volume injected during each treatment session for each subject will be recorded in the CRFs.

CaHA: up to two treatment sessions at 4-week interval with the required first treatment at Visit 1 and an optional second treatment at Visit 3 to achieve an optimal cosmetic correction. Each treatment session will be consisted of multiple subdermal injections, up to 1.5 mL/session (or up to 0.75 mL/NLF/session), into the left and right NLFs of each subject according to the IFU. The second treatment is optional and will be determined based on the Investigator assessment. If the subject needs a second treatment, an appropriate amount will be determined at the Investigator discretion to achieve an optimal outcome. The amount of each treatment needs to be equal at the left and right NLFs because of the identical WAS scores. The treatment volume injected during each treatment session for each subject will be recorded in the CRFs.

8. TREATMENT OF SUBJECTS

8.1 Informed Consent Form

An IRB-approved informed consent form (ICF) will be given to each prospective subject before participation in any study procedures. Prospective subjects will be given as much time as needed to read the ICF and will have the opportunity to have any study-related questions answered to their satisfaction prior to signing the ICF. If further questions exist, prospective subjects will be given sufficient time during the visit to have questions regarding the study and/or the ICF answered by the Investigator or study coordinator prior to signing.

8.2 Subject Identification

Enrolled subjects will be assigned a number that will uniquely identify every subject on the study. The numbers will remain with the subject throughout the study and should be used in all references to the individual in this study.

8.3 Subject Instructions for the Study

Subjects must show up to the study site with clean face without any makeup. Male subjects with facial hair must shave prior to any study visit.

Protocol GLI.04.US.SL.020

CONFIDENTIAL

Throughout the study, subjects must avoid extended periods of sun exposure and use of tanning beds or sunless tanning products on the face. Extra care should be taken to wear sunscreen and accessories (i.e., hat) and avoid sun exposure from 10 am to 3 pm.

All subjects must follow a provided post-care after biopsy procedure (see Appendix I: Biopsy Procedure and Post-Care).

Subjects in PLLA group needs to massage the injection areas for 5 minutes, 5 times a day for 5 consecutive days after the treatment. Subjects will complete a daily diary, recording time and number of massages to ensure treatment compliance.

9. STUDY PROCEDURES

There will be 5 visits during the course of the study:

1. Visit 1 – Screening/Day 0/Baseline
2. Visit 2 – Day 5
3. Visit 3 – Day 28 (Week 4)
4. Visit 4 – Day 84 (Week 12)
5. Visit 5 – Day 89

Test design / flow chart	Visit 1	Visit 2	Visit 3	Visit 4	Visit 5
Informed consent	X				
Photo consent	X				
Demographics/Med History	X				
Concomitant Meds.	X				
Inclusion and exclusion criteria	X				
UPT	X		X		
Randomization	X				
Case report form (CRF)	X	X	X	X	X
3D clinical photography	X		X	X	
Punch biopsy	X			X	
Treatment product injection	X		X*		
Stitch removal		X			X
AE Reporting	X	X	X	X	X

*PLLA group required for a second treatment. CaHA group for an optional touch-up.

9.1 Visits and Examinations

9.1.1. Visit 1 (Screening/D0/Baseline)

1. Subjects will report to the testing clinic at D0 for baseline screening.
2. Subjects will be screened and qualified on the basis of the subject inclusion and exclusion criteria. Subjects failing to meet criteria will be dismissed from the study.

Protocol Version: 04

This document contains confidential, proprietary information.

Protocol GLI.04.US.SL.020

CONFIDENTIAL

3. Prior to beginning of any study related activities, subjects will be informed about the purpose and nature of the study, the expected post-treatment events, and the potential risks involved with the treatments.
4. Subjects will be given an informed consent form, HIPAA form, and photography release form to read.
5. Once subjects have completed reading, they will be interviewed to ensure their understanding of the aforementioned forms and be given the opportunity to ask any study related questions.
6. Subjects who agree to sign the aforementioned forms will be asked to complete a demographic information, medical history form, and concomitant medication form. Subjects declining to sign any of the forms will be dismissed from the study.
7. Female subjects will need to perform UPT to confirm childbearing potential.
8. Subjects will be assigned to a treatment group and side of punch biopsy at the NLF based on the predetermined computer-generated randomization.
9. Subjects will participate in the following procedures completed by the Investigator or a trained clinic staff:
 - a. 3D clinical photography by Cherry Imaging of full face as described in section 10.2
 - b. A 3-mm punch biopsy at the assigned side of the NLF as described in section 10.3
10. Investigator will then instruct the subjects on the assigned treatment administration procedure and perform the treatment into both left and right NLFs.
11. Investigator or clinic staff will record the details of the administration, amount of each treatment used for each NLF and any subsequent adverse events (AEs) in the CRF.
12. Subjects will be instructed on any standard care post-biopsy and post-treatment, and when to contact the Investigator in case of emerging AEs.
13. Subjects will be scheduled to return to the clinic in 5 days (± 1 day) and dismissed from the clinic.

Note: Whenever possible, the same Investigator/staff that perform the baseline assessments and treatments should perform these assessments for each individual subject for the entire duration of the study. In the event of a change in the assigned Investigator/staff for a given subject, the reason for change must be documented.

9.1.2. Visit 2 (D5 ± 1 day)

1. Clinic staff or Investigator will record any AEs that are observed or reported.
2. Investigator will examine the wound and remove any suture from the biopsy site.
3. Subjects will be scheduled for a follow-up visit at Day 28 or Week 4 (± 3 days) and be dismissed from the clinic.

9.1.3. Visit 3 (D28/W4 ± 3 days)

1. Clinic staff or Investigator will record any AEs that are observed or reported.
2. Female subjects will need to perform UPT to confirm childbearing potential.
3. All subjects will have 3D clinical photography by Cherry Imaging taken of full face as described in section 10.2.
4. For PLLA group, subjects will have a second treatment into both left and right NLFs performed by the Investigator.
5. For CaHA group, Investigator will assess and perform an optional touch-up on both NLFs to reach the optimal aesthetic result.

Protocol Version: 04

This document contains confidential, proprietary information.

Protocol GLI.04.US.SL.020

CONFIDENTIAL

- a. If touch-up is needed, the same study treatment and type of injection technique for the baseline treatment need to be used for this step. The amount of treatment can differ compared to Visit 1; however, it needs to be the same for the left and right NLFs.
 6. Investigator or Clinic staff will record the amount of the treatment used for the NLFs in the CRFs.
 7. Once completed, subjects will be scheduled for a follow-up visit at Day 84 or Week 12 (± 3 days) and be dismissed from the Clinic.
- 9.1.4. Visit 4 (D84/W12 ± 3 days)
1. Clinic staff or Investigator will record any AEs that are observed or reported.
 2. Subjects will participate in the following procedures completed by the Investigator or a trained clinic staff:
 - a. 3D clinical photography by Cherry Imaging of full face as described in section 10.2.
 - b. A 3-mm punch biopsy at the other side of the NLF as described in section 10.3.
 3. Subjects will be scheduled for a follow-up visit at Day 89 (± 1 day) and be dismissed from the clinic.
 4. Once completed, subjects will be dismissed from the Clinic.
- 9.1.5. Visit 5 (D89 ± 1 day)
1. Clinic staff or Investigator will record any AEs that are observed or reported.
 2. Investigator will examine the wound and remove any suture from the biopsy site.
 3. Investigator will assess both biopsy sites on scarring potential. If needed, the Investigator will offer a subsequent laser treatment session to minimize scars.
 4. If laser treatment is not needed, subjects complete the study and will be dismissed from the clinic.

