APPENDIX I: BIOPSY PROCEDURE AND POST-CARE**1. Biopsy Visits**

- a. Prepare the Area to be Biopsied
 - i. After the patient, guardian, and/or power of attorney have been consented, initials are completed the area of skin where biopsy will be performed needs to be identified and circled with surgical marker. Once area is identified – a photo of area being biopsy is mandatory. Next, the area of skin where the biopsy is taking place will be prepared with an alcohol swab to ensure sterile conditions prior to procedure.
- b. Anesthetize the Skin
 - i. Once the skin has been identified, photo is taken, and prepared with alcohol swab - the next step is to anesthetize the area to be biopsied by injecting a solution of Lidocaine 1% and Epinephrine or Lidocaine 1% with no Epinephrine (if patient is allergic to Epinephrine or breast feeding) just under the epidermis (sub-epidermally) using a Syringe. The slight burning will quickly subside and the site will become numb. Once area has been anesthetized, it is critical for area to be tested to make sure the area of skin being biopsy is indeed numbed.
- c. Biopsy the Skin
 - i. After the area to be biopsied is anesthetized, the biopsy continues. Using a sterile 3 mm skin punch, the study investigator applies pressure and twisting in a “drilling” motion until the blade of the skin punch has pierced the epidermis of the skin.
 - ii. After the blade has sufficiently “cored” or carved out a 3mm cylinder of skin the punch is removed.
 - iii. Nurse assists with hemostasis- gauze, gloves, etc. for bleeding purposes. Once specimen is removed by provider, 1-3 sutures will follow.

2. Post-Biopsy Procedure

- a. Keep the initial dressing/bandage in place and dry for up to 24 hours.
- b. Change the dressings 2 times a day using the following method.
 - i. Wash your hands before and after changing the dressings.
 - ii. Clean the affected area gently with mild soap. If you have stitches, you may use cotton tipped applicators (Q-tips) around the stitches. It is okay if the stitches get wet in the shower after the first 24 hours.
 - iii. Gently pat dry the area.
 - iv. Apply antibiotic ointment (Polysporin, Bactroban, Mupirocin, Gentamicin, Neosporin, Aquaphor, Vaseline) to the affected area.
 - v. Cover with Band-Aid or telfa pad (non-stick) dressing and tape.
- c. Repeat this process daily until the wound is healed (usually 5-7 days) or the stitches are removed.

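### A second biopsy on Day 87 leaves only 1 to 3 days before in-window stitch removal, against 4 to 6 days after the first biopsy

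*Combined protocol and SAP*

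**What the plan says.** The second biopsy is taken at Visit 4. The Section 9.1.4 heading, "Visit 4 (D84/W12", carries a window of ±3 days. Item 3 of that section then fixes the next visit: "Subjects will be scheduled for a follow-up visit at Day 89", ±1 day. The Section 9.1.5 heading, "9.1.5. Visit 5 (D89", repeats this ±1-day window, and sutures come out at that visit. The Synopsis entry for Visit 5, labelled D89, says "All subjects will return to the site to remove surgical stitch at the biopsy site". The Synopsis and the visit list in Section 9 give only the nominal day, and neither links Visit 5 to the date on which Visit 4 took place.

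For the first biopsy, Section 9.1.1 item 13 counts forward from the procedure visit: "Subjects will be scheduled to return to the clinic in 5 days", ±1 day. At Visit 2 (Section 9.1.2), "Investigator will examine the wound and remove any suture from the biopsy site".

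Appendix I, which Section 8.3 tells subjects to follow, gives 5 to 14 days for suture removal, depending on the body area. On dressing changes it says "Repeat this process daily until the wound is healed (usually 5-7 days) or the stitches are removed".

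On what follows Visit 5, Section 9.1.5 item 4 says "If laser treatment is not needed, subjects complete the study and will be dismissed from the clinic".

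**The concern.** Visits 4 and 5 each have a window around a fixed study day, and the Visit 4 window is the wider of the two. A late Visit 4 therefore shortens the time to stitch removal, because Visit 5 does not move with it. The first biopsy cannot have this problem: Day 0 has no window.

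Both wounds come from the same 3-mm punch in a nasolabial fold, on opposite sides, so one would expect the same healing time before the stitches come out. At the late edge of the Visit 4 window, a site that follows the protocol exactly must remove facial stitches sooner than the study ever allows after the first biopsy. The alternative is to record a departure from the Visit 5 window.

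Visit 5 is also where both biopsy sites are assessed for scarring potential, so a late second biopsy means an earlier look at that wound.

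**Working it through.** **Inputs**
- First biopsy: Day 0 (Sections 9.1.1 and 10.3).
- First stitch removal: Day 5 ±1, so Days 4 to 6 (Section 9.1.1 item 13; Section 9.1.2).
- Second biopsy: Day 84 ±3, so Days 81 to 87 (Section 9.1.4).
- Second stitch removal: Day 89 ±1, so Days 88 to 90 (Section 9.1.4 item 3; Section 9.1.5).
- Suture-removal interval in the post-care instructions: 5 to 14 days (Appendix I).

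**Formula:** gap = stitch-removal day − biopsy day.

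**Nominal schedule.** First biopsy: 5 − 0 = 5 days. Second biopsy: 89 − 84 = 5 days. The nominal days agree, so any mismatch comes from the windows.

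**First biopsy, in window.** 4 − 0 = 4 to 6 − 0 = 6, so 4 to 6 days.

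**Second biopsy, in window**

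| Visit 4 day | Gap to Day 88 | Gap to Day 89 | Gap to Day 90 | Can reach 4 days? |
|---|---|---|---|---|
| 81 | 7 | 8 | 9 | Yes |
| 82 | 6 | 7 | 8 | Yes |
| 83 | 5 | 6 | 7 | Yes |
| 84 | 4 | 5 | 6 | Yes |
| 85 | 3 | 4 | 5 | Yes, if booked on Day 89 or 90 |
| 86 | 2 | 3 | 4 | Only if booked on Day 90 |
| 87 | 1 | 2 | 3 | No |

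Of the 21 in-window pairs of days, 6 fall below 4 days, 9 give 4 to 6 days and 6 exceed 6 days. Day 87 is the only biopsy day with every gap below 4. Its shortfall is 4 − 3 = 1 to 4 − 1 = 3 days.

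**Departure needed to wait longer**
- 4 days after Day 87: 87 + 4 = Day 91, which is 91 − 90 = 1 day past the window.
- 5 days after Day 87: 87 + 5 = Day 92, which is 92 − 90 = 2 days past.
- 5 days after Day 86: 86 + 5 = Day 91, which is 1 day past.

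**Against the Appendix I lower limit of 5 days.** The longest in-window gap is 4 days after Day 86 and 3 days after Day 87, so two of the seven biopsy days cannot comply. Visit 2 on Day 4 falls short of that limit as well.

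**With Visit 5 set at the actual Visit 4 date + 5 ±1 days.** The gap is 4 to 6 days for all seven biopsy days. Visit 5 then falls between 81 + 4 = Day 85 and 87 + 6 = Day 93. The stated 13 weeks is 13 × 7 = 91 days, so the latest date runs 93 − 91 = 2 days over.

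**The case against.** The strongest objection is to the benchmark. The protocol nowhere states 4 days as a wound-care limit; it is the early edge of the Visit 2 window. The only explicit interval from biopsy to suture removal is Appendix I's 5 to 14 days. Section 8.3 makes that appendix binding on subjects, although some of its wording is that of a general clinic handout. This is right as far as it goes, but using Appendix I instead makes the problem larger: Day 86 fails along with Day 87.

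A second objection is that the effect in practice is small. Visit 5 is booked once the biopsy date is known, the investigator examines the wound before removing anything, and a one-day departure is enough to reach 4 days. Subjects are also told to contact the provider about wound problems. All of this stands and keeps the point minor. It does not reconcile the two windows, because the remedy is still a departure from the written schedule.

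A third is that anchoring Visit 5 at 5 ±1 days rules out the gaps of 7 to 9 days now possible after biopsies on Days 81 to 83, all of which Appendix I accepts. That is a real cost, and it is counted with the fix.

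Finally, the absence of a scheduled visit after Visit 5 (unless laser treatment is needed) applies to every subject, whatever the Visit 4 date. It means a wound problem after early removal would not be picked up at a later scheduled visit, as Visit 3 could do after the first biopsy. The windows do not cause this, and the fix does not change it.

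**Conclusion.** The point holds, and it is minor. No stated calculation is wrong, but the Visit 4 and Visit 5 windows do not fit together at the late end. Judged by the interval the study allows after the first biopsy, one permitted biopsy day of seven (Day 87) has no acceptable in-window removal date. Judged by Appendix I, two of seven (Days 86 and 87) have none. These are counts of calendar days, not expected proportions of the 20 subjects.

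The conclusion assumes that Visit 5 is scheduled by study day, as written, and that the two wounds should have comparable healing time. The protocol does not say how often Visit 4 will fall on Day 87 or what harm removal at 1 to 3 days would cause, so neither is estimated here. The gene-expression and volume comparisons are untouched, because their final measurements are taken at Visit 4.

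**What to change.** In Section 9.1.4 item 3 and the Section 9.1.5 heading, define Visit 5 as 5 days (±1 day) after the actual date of the Visit 4 biopsy, and keep Day 89 as the nominal label. The matching line in the table of contents changes too. The Synopsis and visit list show only the nominal day and can stay.

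The cost is a protocol amendment under Section 14.4, with no added visit. Each subject keeps a three-day window, but across subjects Visit 5 would fall on Days 85 to 93 instead of Days 88 to 90, at most 2 days beyond the nominal 13 weeks. Gaps of 7 to 9 days after an early Visit 4 would no longer be in window.

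As a separate option, if the investigator prefers Appendix I's 5-day lower limit, set both stitch removals at 5 days (+1 day) in place of ±1. That also means editing Section 9.1.1 item 13, the Section 9.1.2 heading and its contents line. Visit 2 would narrow to Days 5 to 6, and Visit 5 would fall between 81 + 5 = Day 86 and 87 + 6 = Day 93.
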